13.3. Time to Rescue therapy

Time to rescue therapy will be defined as the time to the start date of the first reported administration of steroid treatment, per the Steroid Treatment CRF, that is reported as “Rescue” for the Timing of Use variable.

For subjects who **will be positively assessed for the need of rescue therapy**, the time to rescue therapy will be calculated as:

Time to rescue therapy (days)

$$= \text{Start date of first rescue treatment} - \text{Date of Visit 2 (Baseline (Day 1))} + 1$$

In cases of **study discontinuation or a subject completing study without the need for rescue therapy**, the time will be calculated as follows:

Time to rescue therapy (days)

$$= \text{Date of study completion/discontinuation} - \text{Date of Visit 2 (Baseline (Day 1))} + 1$$

Time to rescue therapy will be presented in a listing.

13.4. BP Disease Area Index

Observed values and change from baseline in total BPDAl activity score, BPDAl activity subscales, and total BPDAl damage score at End of Treatment (EOT)/disease control will be summarized between treatment groups using descriptive statistics. The change from baseline summarization at EOT will include the EOT assessment reported for ITT subjects. The summary at disease control will include the EOT visit results from subjects who achieved disease control during Weeks 1-3.

Both the activity score and the damage score are the arithmetic sums of their components (see Protocol section 7.1.1.3.1). For the activity score, each item in each of the lists Skin Erosions/Blisters, Skin

Version: 1.0

Protocol version: 4.0

Urticaria/Erythema/Other and Mucosa Erosion/Blisters is graded from 0 to 10 (see Protocol section 17.1 for the items and possible grades), and all items' grades are summed. The score reported in the eCRF question "Total BPDAI Activity Score" is used for analyses. For the damage score, each item in the Skin list is graded with 0 or 1 (see Protocol section 17.1 for the items), and the grades summed. The score reported in the eCRF question "Total BPDAI Damage Score" is used for analyses.

Total BPDAI activity score, total BPDAI damager score, the subscales used to calculate the total BPDAI activity score and total BPDAI damage score (as well as change from baseline in these values) will be provided in a listing; the individual assessments collected on the CRF for BPDAI will also be presented in the listing.

13.5. Pruritus

Change from baseline in total BPDAI-VAS score will be summarized in the same manner as the total BPDAI activity score. Observed values and mean change from baseline is calculated by treatment group and summarized at each visit where parameters were scheduled to be collected using descriptive statistics. Analysis at Visit 5 (Week 3) will include those subjects who reach Week 3 without early termination or reaching disease control; EOT is summarized collectively in a separate analysis visit. A figure plotting subject level change from baseline in total BPDAI-VAS score will be reported for each post-baseline time point where BPDAI-VAS is scheduled to be collected per the clinical study protocol. A plot presenting change from baseline in BPDAI-VAS total scores at each post-baseline time point will also be provided by treatment group. A listing of the total BPDAI-VAS score, change from baseline in total BPDAI-VAS score, as well as the individual questions used to calculate the score, will also be provided.

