15 SCHEDULE OF EVENTS

	Screening/ Baseline		Treatment			EOT	Safety Follow-up ⁶
Visit Number/Name	1	2	3 ¹	4 ²	Unsched. Visit ⁴	5 ³ / EOT ⁵ 21 or Dis. Control ±2 ³ Up to 3	Follow-up EOT + 14 ±3 Up to 5
Day	-3 to 0	1	7	14			
Window (days)			±2	±2			
Week			1	2			
Informed consent ⁷	X						
Demographics	X						
Medical history	X						
Inclusion/exclusion criteria	X	X ⁸					
Physical examination	X					X	
Targeted physical examination		X	X	X			
Vital signs	X	X	X	X		X	
12-lead ECG	X						X
BPDAI	X	X	X	X			X
BPDAI-VAS	X	X	X	X			X
Skin biopsy ⁹	X						X
Blister fluid collection		X	X				
Randomization		X					
Topical steroid assessment ¹⁰		X			X		
Administration of study agent		↔					
Administration of topical steroid therapy		↔					
Assessment of disease control ¹¹			X	X	X	X	
Rescue therapy assessment ¹²			X	X	X		
MoCA		X					X
DLQI		X					X
Laboratory tests ¹³	X	X	X	X			X
Serum protein sample collection	X	X	X	X			X
Anti-BP180 antibodies sample collection	X	X	X	X			X
Pregnancy test (in WOCBP only) ¹⁴	X						X
PK blood sample ¹⁵		X	X	X			X
Biomarker plasma aliquots ¹⁶		X					X
Study agent accountability ¹⁷		X	X	X	X		X
Adverse events	X	X	X	X	X	X	X
Concomitant medications ¹⁸	X	X	X	X	X	X	X
Documentation of confirmation of histological BP diagnosis						X	
Trial completion							X

Notes:

1. At Visit 3/Week 1, all subjects that have not achieved disease control will be assessed for rescue therapy. Rescue therapy is indicated if the subject worsens at any time during the study or fails to improve by the end of Week 1, as assessed by the investigator.
2. After Visit 3/Week 1, subjects will continue to be assessed weekly until disease control/EOT visit.
3. Subjects that do not reach disease control by the end of Week 3/Visit 5 will be discontinued and required to perform all EOT visit procedures. Visit 5 will be the EOT visit for subjects that reach Week 3, and all EOT procedures will be performed. The visit window of \pm 2 days is applicable only for subjects that did not yet reach disease control and are being discontinued. Subjects that reach disease control should complete EOT on the same day in which disease control is confirmed.
4. Unscheduled visits can be performed during the study for assessment of AEs, concomitant medications, or disease control, but are not to be conducted in place of a scheduled weekly visit.

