5. All EOT visit procedures will be conducted at any point in the study once the subject has achieved disease control. This may be performed outside of the scheduled weekly visits and in place of the next scheduled visit.
6. Trial completion will occur after the completion of the Safety Follow-up call. The Safety Follow-up call should occur 14 days \pm 3 days following the EOT visit, independent of the actual study day number.
7. All subjects must sign an informed consent consistent with ICH GCP guidelines prior to any trial related procedures, which includes medication washouts and restrictions.
8. At Visit 2/baseline, confirmation of all inclusion and exclusion will be required prior to enrollment in the study.
9. Skin biopsy at screening is required for subsequent confirmation of diagnosis. Skin biopsies at disease control will be performed only if blisters are present and are optional.
10. At baseline, subjects will be assessed by the investigator to assign the initial dose of topical MFC. The dose selected at baseline will be the same dose used throughout the study, unless the subject requires rescue therapy.
11. Disease control is defined as: \leq 3 new blisters/day and healing of existing blisters. Assessment of disease control will be performed during scheduled weekly visits by the investigator, as per protocol. Additional assessments performed daily as part of SOC will be reviewed by the site staff at each study visit to monitor disease progression between visits. SOC assessments of disease control will be collected and recorded, as available.
12. Rescue therapy can be provided at any time after enrollment if the subject's clinical condition worsens OR fails to improve after completing 1 week of treatment, as determined by the investigator.
13. Laboratory tests include: hematology; chemistry; serology (HBV, HCV, HIV, and TB); coagulation; urinalysis. Note: serology will only be conducted at screening. See [Section 7.1.1.2.6](#) for more details.
14. Serum pregnancy test will be collected at screening and end of treatment in WOCBP.

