10.3. Data transformations and derivations

Values will be presented for all scheduled study visits according to the nominal visit obtained from the eCRF. If an unscheduled visit falls in a visit window with an existing nominal visit assessment, the nominal assessment will be used in analyses. If no nominal visit assessment exists for a visit window with unscheduled visit(s), then the first unscheduled visit within the visit window will be used.

If the End of Treatment visit is performed in place of a scheduled weekly visit, the measurements of the End of Treatment visit are also used for that scheduled weekly visit. This is assumed to be the case if the End of Treatment visit falls into the protocol-specified visit window of some scheduled visit, and that particular scheduled visit is not done.

All heights will be converted to centimeters, all weights to kilograms, and all temperatures to Celsius units.

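### Does the Week 3 pruritus summary in SAP 13.5 leave out subjects whom SAP 10.3 would put in?

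*SAP*

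**What the plan says.** SAP 13.5 summarises BPDAI-VAS by treatment group at each scheduled visit. For the last one it says: "Analysis at Visit 5 (Week 3) will include those subjects who reach Week 3 without early termination or reaching disease control". It continues: "EOT is summarized collectively in a separate analysis visit". It states no comparable restriction for Weeks 1 and 2, and it does not mention SAP 10.3.

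SAP 10.3 sets the general rule: "Values will be presented for all scheduled study visits according to the nominal visit obtained from the eCRF". Where an EOT visit replaces a weekly visit, "the measurements of the End of Treatment visit are also used for that scheduled weekly visit". The trigger is that the EOT visit falls in the protocol window of a weekly visit that was not done. The reason for EOT plays no part.

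Note 3 to the Schedule of Events (Protocol section 15) says: "Visit 5 will be the EOT visit for subjects that reach Week 3, and all EOT procedures will be performed". The same note says that the two-day window "is applicable only for subjects that did not yet reach disease control and are being discontinued", and that controlled subjects complete EOT on the day control is confirmed. Protocol 7.3.3.4 carries one heading for EOT, Visit 5 and Week 3 (Day 21 ± 2).

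For BPDAI, SAP 13.4 says: "The change from baseline summarization at EOT will include the EOT assessment reported for ITT subjects". It adds a summary at disease control. SAP 13.5 says BPDAI-VAS is handled in the same manner.

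**The concern.** At first sight the two SAP sections give different Week 3 sets. Take a subject whose control is confirmed on Day 21. Under 10.3 the EOT score counts as Week 3. Under 13.5, if disease control up to and including that visit disqualifies, it does not.

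The strict reading would also have a substantive effect. The Week 3 means and plots by arm would contain only subjects who had not responded, a group selected after randomisation on a component of the primary endpoint. Two programmers could produce different tables from the same data. With six subjects, one person more or less changes an arm's count and mean visibly. Note 3 adds a further doubt, because it is unclear whether a controlled subject on Day 19, 20, 22 or 23 is inside the window that 10.3 relies on.

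**Working it through.** The plan gives no figure on this point to reproduce. The check compares the rules by type of subject and then sizes the difference.

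**Rule comparison**

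| Subject | SAP 10.3 | SAP 13.5 |
|---|---|---|
| EOT for control before Day 19 | not in Week 3 | not in Week 3 |
| Uncontrolled and still in the study at Visit 5 | in | in |
| Control confirmed, with EOT, in the Week 3 window | in, if the window applies | in if the condition means before Week 3; out if it means up to and including Visit 5 |

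Only the third row can conflict, and only under one reading. That reading is the less natural. Note 3 uses the same idea of subjects who reach Week 3 for those still on treatment then. Protocol 5.4.1 also withdraws uncontrolled subjects after three weeks, so counting every exit at Visit 5 against a subject would leave the Week 3 set nearly empty.

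**What the sentence is for.** Visit 5 and EOT share one column in the schedule and one heading in Protocol 7.3.3.4. A Day 9 EOT could therefore carry the Visit 5 label in the eCRF. The sentence in 13.5 keeps such early EOTs out of Week 3. Weeks 1 and 2 have visits of their own and need no such sentence.

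**Chance that anyone is affected.** Inputs: six subjects (SAP 10.1); an assumed proportion p controlled by Day 21, from 0.2 to 0.9; a constant daily chance of control. With q = 1 − p:

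- First control on Day 21: q^(20/21) − q. For p = 0.2 this is 0.0085, and for p = 0.7 it is 0.0177. At least one of six: 1 − (1 − 0.0085)^6 = 0.050 and 1 − (1 − 0.0177)^6 = 0.102.
- First control on Days 19 to 21: q^(18/21) − q, which is 0.0259 and 0.0563. At least one of six: 0.146 and 0.294.

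The chance peaks near p = 0.65, where it is hardly higher than at p = 0.7. If control could be declared only on Days 7, 14 and 21, the chance would be 0.32 to 0.62. That case is unlikely: Protocol 7.1.1.2.3 and SAP 13.2 describe daily assessment, and the former calls for the EOT visit whenever control is indicated.

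**Leverage of one subject.** Adding one subject whose change differs by d from the mean of k others moves the arm mean by d/(k + 1). With d = 3 to 12 points and an assumed three per arm, the shift is 1.0 to 4.0 points for k = 2 and 1.5 to 6.0 for k = 1. With k = 0, the arm has no Week 3 value under the strict reading.

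**Average effect on the arm difference.** Assumed model: 40% against 70% controlled by Day 21, and VAS change = −8 − 3z + N(0, 3), where z is a latent speed of control. Simulation gives a Week 3 difference of −0.78 under the strict reading, −0.80 with Day 21 controllers added and −0.84 with Day 19 to 21 controllers added, a change of 0.02 to 0.06.

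The mapping from z to days matters, so a closed form is a useful check. Take z normal with unit variance and mean μ = Φ⁻¹(0.4) = −0.253 or Φ⁻¹(0.7) = 0.524. The slowest fraction Q of an arm then has mean z of μ − φ(Φ⁻¹(Q))/Q.

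- Strict reading (Q = 0.6 and 0.3): −0.897 and −0.635, so the difference is −3 × 0.263 = −0.79.
- Day 21 added, constant daily chance (Q = 0.615 and 0.318): −0.875 and −0.598, giving −0.83.
- Days 19 to 21 added (Q = 0.645 and 0.356): −0.830 and −0.522, giving −0.92.

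The change here is 0.04 to 0.14. If itch has no link to speed of control within an arm, all the versions equal −3 × (0.524 + 0.253) = −2.33 and the choice makes no difference.

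**The case for a change.** The best case for amending 13.5 has three parts. First, a subject whose EOT came before the Week 3 window has no Week 3 value, so on the milder reading the restriction seems to do almost nothing; that suggests the strict reading was meant. Second, the strict reading need not empty the set: 13.5 speaks of early termination, Week 3 is the planned last treatment visit, and SAP 13.2 distinguishes discontinuation from reaching the end of the study uncontrolled. Third, even the milder reading needs a boundary, and note 3 does not settle it for controlled subjects. A clarifying clause would cost little.

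The first part overlooks the shared Visit 5 and EOT label, which gives the sentence real work on the milder reading. The second stands as far as it goes: the near-empty set is a strong hint and not proof. The third stands too, and the window for a controlled subject on Day 19, 20, 22 or 23 is open. These points establish an ambiguity, not a contradiction. They do not show that any conclusion of the trial depends on it. Note 11 does say "Assessment of disease control will be performed during scheduled weekly visits by the investigator, as per protocol", but it also provides for daily review, so it does not support treating control as a weekly event.

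**Conclusion.** This is a gap that analysts can fill sensibly. On its natural reading SAP 13.5 agrees with SAP 10.3; what remains is whether one subject controlled around Day 21 is shown at Week 3. Under the daily model the chance that such a subject exists among the six is about 5% to 10% for Day 21 alone and 15% to 29% for Days 19 to 21. Those figures, the leverage of 1 to 6 points and the average effect of 0.02 to 0.14 points on a 30-point scale all rest on assumed inputs; only the six subjects and the scale come from the documents.

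Nothing is lost whichever way the table is programmed. The score still enters the EOT summary, the summary at disease control, the subject-level figure and the listing, and n is reported with every continuous summary (SAP 10.1). Protocol 10.2 plans no formal testing, and the SAP limits efficacy to description. Selection at Week 3 comes mainly from the design: treatment ends at control, so earlier responders have no Week 3 value under either reading.

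Simply deleting the restriction could do harm, because an early EOT labelled Visit 5 might then be counted as Week 3. Making EOT the main display between arms, or relabelling the plots, would be a matter of preference, since EOT is already summarised separately. No change to the plan is needed.

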13.6. Skin (biopsy) [REDACTED] count

Skin (biopsy) [REDACTED] counts are collected during skin biopsy at screening and at disease control (optional – only if blisters are present). Observed values and change from baseline in skin biopsy [REDACTED] levels at disease control will be summarized by treatment group using descriptive statistics. A data listing of individual skin [REDACTED] levels will be reported.

13.7. Steroid exposure

Descriptive statistics for total cumulative steroid exposure (cortisol equivalent/kg) will be summarized by treatment group. Steroid treatments will be standardized for their respective cortisol equivalent unit. To determine per kg exposure, the last subject weight reported prior to the initiation of steroid treatment (as reported by the start date) will be used. Total cumulative exposure will require assessment of the start and end date for each respective steroid treatment, in addition to the frequency reported for the treatment. Subjects that report a frequency of AS NEEDED, UNKNOWN, OTHER or INTERMITTENT will be discussed with the sponsor to determine the appropriate calculation.

A figure plotting the individual steroid exposure (cortisol equivalent/kg) per study day per subject will be presented. Steroid exposure per study day will be determined by an assessment of the start and stop dates reported for each steroid treatment on the Steroid Treatment CRF in combination with the frequency reported; daily exposure will distribute the dosing frequency evenly across the date range defined by the start and stop date for each treatment. A figure presented daily steroid exposure (cortisol equivalent/kg) will also be presented by treatment group. A listing of all steroid treatment administration will also be provided.

13.8. Serum protein levels and serum Anti-BP180 IgG

For each serum anti-BP180 IgG, CBC, and serum protein levels [REDACTED] results will be reported in a listing.

13.9. Blister fluid protein levels

For each blister fluid protein level [REDACTED] results will be reported in a listing.

13.10. Biomarkers in plasma samples

Analysis of biomarkers in plasma samples is not included in this SAP and will be defined in a separate Exploratory Analysis Plan.

13.11. Cognitive assessments

The Montreal Cognitive Assessment total score, as well as the components used to derive the total score, will be presented in a listing.

13.12. Quality of life

The Dermatology Life Quality index score, as well as the components used to derive the score, will be presented in a listing.

14. Pharmacokinetic analyses

Only data from the AKST4290 group will be used for pharmacokinetic analyses.

Data handling methods outlined in study protocol section 17.9.4 will be followed (missing data not included, values below lower limit of quantification replaced with zero, parameter estimates and descriptive statistics only reported when at least 2/3 data are available).

AKST4290 concentration values will be reported in a figure, table and listing by analysis time point.

15. Changes to Methods Planned in the Protocol

As detailed in the protocol, the goal was to enroll a total of approximately 30 subjects with the aim of obtaining 27 evaluable subjects. Due to the treatment limitations, rarity of the disease, coronavirus disease 2019 (COVID-19) pandemic, and expiry of Investigational Medicinal Product (IMP), enrollment ended with a total 6 subjects.

Section 10.3 (Analysis Datasets) of the clinical study protocol includes a Per Protocol (PP) analysis set defined as “a subset of ITT subjects.” This analysis set will not be utilized in the statistical analysis due to the limited enrollment noted previously and the restriction to descriptive analysis of study endpoints.

Section 10.4 (Descriptions of Statistical Methods) of the clinical study protocol outlines analysis of the primary endpoint (Section 10.4.2), secondary endpoints (Section 10.4.3) and exploratory analysis (Section 10.4.6). Due to the limited enrollment in the study, the analysis defined in Section 11 (Summary of study population), Section 12 (Safety analyses), 13 (Efficacy analyses) and 14 (Pharmacokinetic analyses) of the SAP will be utilized.

16. Top-Line Data Presentation

The following assessments associated with the study endpoints, as reported by listings, tables, and figures (where applicable), will be provided as top-line results:

- Disease Control and Rescue Therapy
- BPDAI and BPDAI-VAS
- Adverse events
- Skin biopsy [REDACTED] levels
- Steroid exposure
- Blood [REDACTED] levels

17. References

[REDACTED]	[REDACTED]	[REDACTED]	[REDACTED]	[REDACTED]	[REDACTED]
	[REDACTED]				

A 2D grid of black bars on a white background. The grid has 10 columns and 20 rows. The bars are black and are positioned in a non-overlapping manner. The sizes of the bars vary, and they are scattered across the grid. There is no discernible pattern or meaning to the arrangement of the bars.

1

113. *Leptodora* (Leptodora) *hirsutissima* (L.) Kuntze
Leptodora hirsutissima L.

1

[REDACTED]

1

For more information, contact the Office of the Vice President for Research and Economic Development at [contact] or [contact].

This figure displays a 2D binary image, likely a mask or a specific pattern. It consists of a grid of black and white pixels. The image is characterized by several horizontal bands of black pixels. The most prominent band is at the bottom, which contains a variety of black shapes, including rectangles, L-shapes, and T-shapes. Above this, there are several other horizontal bands of black pixels, each containing different black shapes. The background is white, and the shapes are black. The overall pattern is a complex arrangement of black shapes within a white background.

For more information, contact the Office of the Vice President for Research and Economic Development at [contact] or [contact].

[REDACTED]

A 10x10 grid of black and white squares. The pattern consists of a central 4x4 area with a 2x2 center, surrounded by a 2x2 border, and a 2x2 corner block at the bottom-left. The rest of the grid is white.

For more information, contact the Office of the Vice President for Research and the Office of the Vice President for Student Affairs.

For more information, contact the Office of the Vice President for Research and the Office of the Vice President for Student Affairs.

[REDACTED]

[REDACTED]

[REDACTED]

[REDACTED]

[REDACTED]

A 10x10 grid of black and white squares. The pattern consists of a 3x3 block of black squares in the top-left corner, followed by a 2x2 block of black squares in the top-right corner, and a 2x2 block of black squares in the bottom-left corner. The rest of the grid is white.

Statistical Analysis Plan

Protocol number: AKST4290-221

[figure not shown]
[figure not shown]
[figure not shown]
[figure not shown]
Version: 1.0

Protocol version: 4.0

[REDACTED]

[figure not shown]
[figure not shown]
[figure not shown]
[figure not shown]
[figure not shown]
[REDACTED]

[figure not shown]
[figure not shown]
[figure not shown]
[figure not shown]
[figure not shown]
[figure not shown]

Redacted content (11 rows)

The image consists of five rows, each representing a frame of a sequence. The frames are arranged in a 5x8 grid. The background is white. A black object, which appears to be a car, moves from left to right across the frame. In the first frame, the car is on the far left. In the second frame, it has moved to the right. In the third frame, it is positioned in the center. In the fourth frame, it has moved further to the right. In the fifth frame, it is on the far right. A horizontal black bar is present in the middle of the sequence, spanning from the third frame to the fifth frame. The car is positioned to the left of this bar in the third frame and to the right of it in the fifth frame. The car is also present in the first and second frames, but it is not positioned relative to the bar in these frames.

[figure not shown]
1

[figure not shown]
A 5x5 grid of black rectangles on a white background. The rectangles are arranged in a pattern that tapers to the right. The bottom row contains a single long black rectangle.

[figure not shown]
A thick black horizontal bar with a thin black vertical bar extending downwards from its center.

[REDACTED]	[REDACTED]	[REDACTED]	[REDACTED]
[REDACTED]	[REDACTED]	[REDACTED]	[REDACTED]
[REDACTED]	[REDACTED]	[REDACTED]	[REDACTED]

[REDACTED]

A horizontal bar chart with 10 bars of varying lengths. The bars are black on a white background. The lengths of the bars decrease from left to right. There are two small black squares at the top left of the chart area.
